## 7.0 GVHD CLINICAL STAGING

GVHD clinical staging will be according to the established criteria used for Blood and Marrow Transplant Clinical Trials Network GVHD staging (modified Glucksberg criteria).

	Stage 0	Stage 1	Stage 2	Stage 3	Stage 4
Skin	No rash	Rash < 25% BSA	25-50%	> 50% Generalized erythroderma	Plus bullae and desquamation >5% BSA
Liver	Bilirubin ≤ 2 mg/dl	2.1-3 mg/dl	3.1-6mg/dl	6.1-15mg/dl	>15mg/dl
GI tract	Adult: < 500 ml/day	Adult: 500–1000 ml/day	Adult: 1001–1500 ml/day	Adult: >1500 ml/day	Severe abdominal pain +/- ileus, flank blood or melena (regardless of stool volume)
UGI		Severe nausea/vomiting			

 
For stage 4 GI GVHD, severe abdominal pain is defined as (1) pain that requires opioid use and (2) pain that significantly impacts on performance status as determined by the treating physician
 
Comprehensive GVHD staging guidance is provided in the MAGIC GVHD Staging Guidance.
 
					

### Overall Clinical Grade:

Grade 0	No stage 1-4 of any organ
Grade I	Stage 1-2 skin and no liver or GI involvement
Grade II	Stage 3 skin and/or Stage 1 liver and/or Stage 1 GI
Grade III	Stage 0-3 skin with Stage 2-3 liver and/or Stage 2-3 GI
Grade IV	Stage 4 in any target organ (skin, liver, GI)

## 7.1 ENDPOINT AND RESPONSE CRITERIA

### 7.1.1 Definitions

Evaluable for response: Safety, tolerability, and efficacy of AAT will be assessed from the initiation of the first AAT treatment

Complete Response (CR): All evaluable organs (skin, liver, GI tract) stage 0. For a response to be scored as CR on day 28, the patient must be in CR on that day and have had no intervening additional GVHD therapy.

Partial Response (PR): An improvement in one or more organ involved with GVHD symptoms without worsening in others. For a response to be scored as PR on day 28, the patient must be in PR on that day and have had no intervening additional GVHD therapy.

No response (NR): All responses that are not CR or PR. Patients who receive any systemic GVHD therapy other than the continuation or modification of GVHD prophylaxis, systemic steroids, and topical/non-absorbable oral steroid therapy, will be scored as NR on day 28 regardless of organ staging.

### 7.1.2 Proportion of CR and CR+PR

CR and PR on day 28 are scored in comparison to the patient's acute GVHD staging on the day systemic steroid treatment began.

#### **7.1.3 Steroid refractory GVHD**

Patients who are scored as no response on day 28 of systemic steroid treatment for GVHD **or** who receive additional systemic immunosuppression prior to day 28 (i.e., no response) will be considered steroid refractory. Escalation of steroid doses during treatment for GVHD are not considered in the definition of steroid refractory GVHD.

#### **7.1.4 Steroid discontinuation**

The date of discontinuation of steroid therapy will be recorded.

#### **7.1.5 Lines of GVHD therapy**

Systemic steroids are the first line of GVHD treatment. Any additional systemic immunosuppression treatment to steroid therapy for acute GVHD will be considered 2nd line therapy and considered a failure to respond to steroid treatment. Resumption or changes in GVHD prophylaxis (e.g., substitution of mycophenolate for tacrolimus due to PRES) are not considered new lines of therapy. Topical steroids and non-absorbable oral steroids are not considered new lines of therapy.

#### **7.1.6 Non-Relapse Mortality (NRM)**

Any death that occurs after HCT not attributable to relapse of the underlying disease will be considered a non-relapse death.

#### **7.1.7 Chronic GVHD**

The occurrence of chronic GVHD as defined by NIH consensus criteria requiring systemic treatment, including date of diagnosis, will be recorded.

#### **7.1.8 Relapse**

Relapse, including date of relapse, of the underlying malignancy will be recorded.

### **7.2 SAFETY/TOXICITY DEFINITIONS**

7.2.1 Glassia was generally safe and well tolerated in clinical studies of healthy adult subjects, subjects with AAT deficiency, and type 1 diabetes mellitus. Headache (6%) and dizziness (3%) were reported by >1 subject in two clinical studies in patients with AAT deficiency. There were no toxicities observed in a study of AAT Glassia therapy in patients with steroid-refractory acute GVHD that were felt to be related to AAT administration. Although not previously reported, AAT has potential immunomodulatory activity that theoretically could increase the risk for infection. Known or plausible toxicities that may be related to alpha-1-antitrypsin will be reported.

#### **7.2.2 Systemic Infections**

Infections are common in patients who undergo HCT and generally respond to treatment. Any grade 3 infection as defined by the Blood and Marrow Transplant Clinical Trials Network will be reported. The full table can be referenced in Appendix B.

Grade 3 Bacterial Infections:

- a. Bacteremia with deep organ involvement
- b. Severe sepsis with bacteremia
- c. Fasciitis requiring debridement
- d. Pneumonia requiring intubation
- e. Brain abscess or meningitis without bacteremia

- f. Clostridium difficile toxin positive stool with toxic dilatation or renal insufficiency with/without diarrhea.

Grade 3 Fungal Infections:

- a. Fungemia, including candidemia
- b. Proven or probable invasive fungal infections (e.g. Aspergillus, Mucor, Fusarium, Scedosporium)
- c. Disseminated fungal infections (e.g. multifocal pneumonia, presence of urinary/blood antigen, CNS involvement) with Histoplasmosis, Blastomycosis, Coccidiomycosis or Cryptomycosis
- d. Pneumocystis jiroveci pneumonia

Grade 3 Viral Infections:

- a. Severe VZV infection with either associated coagulopathy or organ involvement
- b. CMV end organ involvement (e.g. pneumonitis, enteritis, retinitis)
- c. EBV Post-transplant lymphoproliferative disorder (PTLD)
- d. Adenovirus with end organ involvement (except adenoviral conjunctivitis or upper respiratory tract disease)
- e. All lower respiratory tract viruses
- f. Viral encephalitis or meningitis

Grade 3 parasitic infections:

- a. Toxoplasmosis involving the CNS
- b. Strongyloides hyperinfection

Non-microbiologically documented infections:

- a. Any acute pneumonia requiring mechanical ventilation
- b. Severe sepsis without an identified organism

### 7.2.3 **Viral Reactivations**

Because viral reactivations often require treatment in the HCT population, even in the absence of end organ disease, the following viral infections/reactivations will be reported:

The date, anatomical site or body fluid (e.g., blood, nasopharyngeal swab, stool, etc.), and method of detection for CMV, EBV, HHV6, VZV, HSV and adenovirus will be reported.

## 7.3 **Safety/Tolerability**

Analyses will be performed for all patients having received at least one dose of study drug. The study will use the CTCAE version 4.0 for reporting of adverse events (<http://ctep.cancer.gov/reporting/ctc.html>).

## 8.0 **ADVERSE EVENTS**

### 8.1 **ALPHA-1-ANTITRYPSIN**

For the most recent safety update, please refer to the current Investigator's Brochure or Study Agent Prescribing Information.

#### 8.1.1 Contraindications

Patients who have had an allergic reaction to alpha-1-antitrypsin

#### 8.1.2 Special Warnings and Precautions for Use

Severe hypersensitivity and anaphylactic reactions may occur in IgA deficient patients with antibodies against IgA and in patients with a history of hypersensitivity to other Alpha1-AT products. These reactions are not expected in this study because of the immunosuppressive nature of the transplant procedure.

May carry a risk of transmitting infectious agents such as viruses, the variant Creutzfeldt-Jakob disease (vCJD) and theoretically, the Creutzfeldt-Jakob disease (CJD) agent.

### 8.2 Adverse Event Reporting Requirements

Adverse event (AE) monitoring and reporting is a routine part of every clinical trial and is done to ensure the safety of subjects enrolled in the studies as well as those who will enroll in future studies using similar agents. Data on adverse events will be collected from the time of the initial study treatment (day 0) through 30 days after the last dose of alpha-1-antitrypsin. Any serious adverse event that occurs more than 30 days after the last alpha-1-antitrypsin dose and is considered related to the study treatment must also be reported. Serious Adverse Events (SAEs) will continue to be followed until:

- Resolution or the symptoms or signs that constitute the serious adverse event return to baseline;
- There is satisfactory explanation other than the study treatment for the changes observed; or
- Death.

The investigator is responsible for the detection, documentation, grading and assignment of attribution of events meeting the criteria and definition of an AE or SAE. The definitions of AEs and SAEs are given below. It is the responsibility of the principal investigator to ensure that all staff involved in the trial is familiar with the content of this section.

Any medical condition or laboratory abnormality with an onset date before initial study treatment administration is considered to be pre-existing in nature. Any known pre-existing conditions that are ongoing at time of study entry should be considered medical history.

All events meeting the criteria and definition of an AE (CTCAE grade 3 or higher) or SAE, as defined in Section 8.3, occurring from the initial study treatment administration through 30 days following the last dose of the study treatment or study intervention must be recorded as an adverse event in the patient's source documents and on the CRF.

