#### **Secondary endpoints:**

1. Overall survival at 6 months
2. Cumulative incidence of NRM at 6 months and 1 year
3. Relapse rate (see section 2.2.1)

4. 100 days incidence of clinically relevant GVHD states including steroid-refractory GVHD, grade II-IV GVHD, and grade III-IV GVHD (See section 2.2.1).
5. For patients who develop GVHD prior to day 100 post-HCT, the overall response rate (CR + PR) 28 days after initiation of systemic steroid treatment. PR is defined as improvement in one or more organs involved with GVHD symptoms without progression in others. For a response to be scored as PR on day 28, the patient must be in PR on day 28 and have had no intervening systemic therapy for acute GVHD other than steroids.
6. Cumulative incidence of severe GI GVHD stage 3 or 4 by day 100 post-HCT
7. Cumulative incidence of chronic GVHD requiring systemic steroid treatment by one year
8. Number of serious infections (defined as grade 3 by the Blood and Marrow Transplant Clinical Trials Network)

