### 6.3 Time and Events Table

	CALENDAR BASED ASSESSMENTS													GVHD DRIVEN ASSESSMENTS 		
	Screening HCT Day 7 HCT Day 14 	Study day 0	Study day 7	Study day 14	Study day 21	Study day 28	Study day 35	Study day 42	Study day 49	Study day 56	Every other week to HCT Day 100	HCT Day 100	HCT Day 180	1 Year Post HCT	GVHD Diagnosis or Treatment	Weekly x 4 from start of GVHD Diagnosis or Treatment
Windows	+/- 1 day	Within 2 days of Risk Score Notification	+/- 2 days	+/- 2 days	+/- 2 days	+/- 2 days	+/- 3 days	+/- 3 days	+/- 3 days	+/- 3 days	+/- 6 days	+/- 3 days	+/- 14 days	+/- 14 days	+/- 2 days	+/- 2 days
Eligibility Review	X															
Concomitant Medication Review 	X	X	X	X	X	X	X	X	X	X	X	X	X	X	X	X
Adverse Event Evaluations	X	Adverse events will be reported from the time of the study day 0 through 30 days after the last dose of study drug. Report serious adverse events as they occur.														
Serum Chemistry	X															
GVHD Staging 	X	X	X	X	X	X	X	X	X	X	X	X	X	X	X	X
Alpha-1-antitrypsin Administration		90 mg/kg Once	45 mg/kg Twice weekly for 15 more doses for a total of 16 doses.												If GVHD occurs, continue AAT treatment. Complete 16 doses as per protocol.	
Survival, Relapse & Chronic GVHD Status													X	X	X	
CORRELATIVES STUDIES																
Serum Sample (10 mL) 	X	X	X	X	X	X			X (HCT day 56 +/- 3 days, not study day 56)					X	X	

 When GVHD driven assessments and sample collections occur within 3 days of a calendar based assessment/collection, the calendar assessment/collection is not required.

 Screening occurs on day 7 post-HCT and, if still eligible for screening, again on day 14 post-HCT. Screening samples are sent via overnight shipping to the MAGIC laboratory in New York. Patients who do not meet eligibility by high risk biomarkers will be followed for minimum data collection: GVHD onset date, maximum GVHD severity, steroid refractory GVHD by day 100 (Y/N), chronic GVHD requiring treatment (Y/N), relapse and death with reporting once at one year post-BMT.

 Concomitant medication review will record **only** immunosuppressants and other drugs administered during the reporting period for GVHD prevention and treatment.

 GVHD staging will follow the detailed guidelines provided in the MAGIC Acute GVHD Staging Guidance.

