## 8.7 Stopping Rules

Although alpha-1-antitrypsin is generally safe, its use as a pre-emptive therapy for acute GVHD has not been previously studied. We will continuously monitor the incidence of BMT CTN grade 3 infections occurring within 8 weeks of study administration and accrual will be halted if there is sufficient evidence that the infection rate exceeds the acceptable target rate of 24% (the incidence in patients with high risk GVHD) by more than 30%. If the incidence of BMT CTN grade 3 infections occurring within 8 weeks of study administration is greater than the associated boundary value  $b_k$  listed in the table below, among the  $k$  patients enrolled in the trial, then accrual will be halted for safety considerations.

Maximum # of Patients, $k$	6	7-12	13-18	19-24	25-30
Boundary, $b_k$	3	5	7	9	11

Specifically, if more than 3 out of the first 6 patients, 5 out of the first 12 patients, 7 out of the first 18 patients, 9 out of the first 24 patients, or 11 out of the first 30 patients, experience grade 3 infections occurring within 8 weeks of study administration, the trial will be halted for safety considerations.

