## 11.0 STATISTICAL CONSIDERATIONS

### 11.1 Study Design/Study Endpoints

This is a proof of concept pilot single arm, open label multicenter clinical trial. The primary study measure of efficacy is the incidence of steroid-refractory GVHD by Day 100 after HCT. GVHD is defined as steroid refractory if CR or PR is not achieved by day 28 of systemic steroid treatment **OR** if additional immunosuppression beyond steroids was given for treatment of GVHD prior to 28 days of steroid treatment. Subjects who start treatment for GVHD within 28 days of Day 100 (i.e., on or after Day 72 post-HCT) must be followed for a full 28 days of systemic steroid treatment for the purposes of assessing the primary study measure of efficacy.

Because we expect improvements in the incidence of steroid refractory GVHD to translate into better long-term outcomes, secondary endpoints include 6 month NRM and 6 months overall survival. Additional secondary endpoints related to efficacy will include, in subjects who develop GVHD, time to discontinuation of steroid therapy, number of lines of GVHD therapy, and cumulative incidence of chronic GVHD. Secondary endpoints related to safety include 6 month and 1 year relapse rates and incidence of serious (BMT CTN grade 3) infections by day 100.

The historical control population for this study consists of patients who met the criteria for a high MAGIC GVHD risk score at either day 7 and 14 (see Background).

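### Recording of grade 3 infections is tied to the last AAT dose, but the day-100 infection endpoint and the 8-week stopping rule are not, and no section gives an end date for infections

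*Combined protocol and SAP*

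**What the plan says.** Section 8.2 sets the general window: "Data on adverse events will be collected from the time of the initial study treatment (day 0) through 30 days after the last dose". The Time and Events Table in 6.3 agrees: "Adverse events will be reported from the time of the study day 0 through 30 days after the last dose of study drug". After that, 8.2 asks for much less: "Any serious adverse event that occurs more than 30 days after the last alpha-1-antitrypsin dose and is considered related" to treatment. The last paragraph of 8.2 applies the same 30-day limit to source documents and the CRF, for events as Section 8.3 defines them.

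Two infection measures have windows of their own:

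- Section 8.7, stopping rule: "We will continuously monitor the incidence of BMT CTN grade 3 infections occurring within 8 weeks of study administration". It does not say which dose the 8 weeks start from.
- Section 11.1, secondary safety endpoint: "incidence of serious (BMT CTN grade 3) infections by day 100".

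Three places mention the infections with no end date. Section 7.2.2 says "Any grade 3 infection as defined by the Blood and Marrow Transplant Clinical Trials Network will be reported". Section 8.3.1 says the same of all such infections. The secondary endpoint list after 2.3 counts serious infections without a time limit.

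The calendar in 6.3 has no infection row. Section 5.6 keeps patients who stop AAT in the follow-up of 5.7, but 5.7 and 6.2 speak of GVHD, survival and relapse, not infections.

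**The concern.** A window that ends 30 days after the last dose differs in length between patients. The two infection measures need the same span for everyone. The infection exception sits inside the adverse event definition in 8.3.1, and 8.2 limits recording of events defined in 8.3. A site could therefore reasonably stop recording infections at 30 days, while another site, following 7.2.2, continues.

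Infection is the only event with a formal safety boundary in this trial. An infection that is not recorded can only lower the count, so any loss favours continued accrual and a lower reported infection rate. The loss is greatest in patients who stop AAT early.

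**Working it through.** **Inputs.**
- Recording ends at last dose + 30 days (8.2, 6.3).
- 16 doses, twice weekly over 8 weeks, spaced 2 to 4 days apart, with a ten-week limit (5.1.2 to 5.1.4).
- Start of treatment: in the example in 5.1, a day-7 sample is scored on day 8 and treatment starts by day 10, so HCT day 8-10. The same arithmetic gives HCT day 15-17 for a day-14 sample.
- Day 100 in 11.1 is read as HCT day 100, as for the primary measure in that section.
- Boundaries and stopping probabilities are from 8.7.
- The share of patients who stop AAT early is not in the documents. I assume 0% to 30%.

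**1. The plan's own figures.** An exact binomial recursion that stops when the count exceeds 3, 5, 7 or 9 at 6, 12, 18 or 24 patients gives:

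| True rate | 24% | 30% | 40% | 50% | 54% |
|---|---|---|---|---|---|
| Stated in 8.7 | 0.09 | 0.25 | 0.61 | 0.89 | 0.94 |
| Recomputed | 0.094 | 0.239 | 0.599 | 0.883 | 0.942 |

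Adding the look at 30 patients gives 0.103, 0.270, 0.670, 0.931 and 0.971, which does not match from 40% upwards. I use the first convention below.

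**2. Day-100 endpoint on the 8.2 window.** A full course at average spacing has its last dose at 15 × 3.5 = study day 52.5, so recording ends at 52.5 + 30 = study day 82.5.

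| Start (HCT day) | Full course: recording ends (HCT day) | Days short of 100 | One dose only: days short of 100 |
|---|---|---|---|
| 8 | 90.5 | 9.5 | 62 |
| 10 | 92.5 | 7.5 | 60 |
| 15 | 97.5 | 2.5 | 55 |
| 17 | 99.5 | 0.5 | 53 |

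In the cohort of Section 1.2, 145 of 205 high-risk patients (71%) were identified on day 7, so the larger gap would apply to most patients. Dosing extended to ten weeks is covered: 70 + 30 = study day 100, which is past HCT day 100.

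**3. Stopping rule, 8 weeks counted from first dose.** With last dose on study day L, the 56 days are covered if L + 30 ≥ 56, that is, L ≥ 26.
- Full course: covered to day 82.5. Even at 2-day spacing, 15 × 2 + 30 = day 60.
- Dose 8 at average spacing falls on day 7 × 3.5 = 24.5, which loses 1.5 days. At 4-day spacing it falls on day 28, which loses none.
- Last dose on day 14: 56 − 44 = 12 days lost (12/56 = 0.214).
- One dose only: 56 − 30 = 26 days lost (26/56 = 0.464), the maximum.

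**4. Effect on the stopping probability.** Assume a share f stops early, infections are spread evenly over the 56 days, and a fraction m of the window is lost. Recorded rate = true rate × (1 − f × m). For a true 40%, f = 20% and m = 0.464, this is 0.40 × 0.907 = 0.363.

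| f | True 40%, one dose | True 40%, last dose day 14 | True 54%, one dose | True 54%, last dose day 14 |
|---|---|---|---|---|
| 0% | 0.599 | 0.599 | 0.942 | 0.942 |
| 10% | 0.530 | 0.567 | 0.908 | 0.928 |
| 20% | 0.459 | 0.535 | 0.863 | 0.911 |
| 30% | 0.390 | 0.503 | 0.805 | 0.893 |

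**5. If the 8 weeks run from the last dose instead.** 56 − 30 = 26 days are uncovered in every patient.

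**The case against.** The case for the plan is that specific commitments outweigh a general window. Section 8.7 promises continuous monitoring over its own 8 weeks, and its enrollment rule counts patients still under observation for toxicity, which presupposes follow-up through that window. Sections 7.2.2 and 8.3.1 set no dose-based limit and no relatedness condition for these infections. Serious infections are listed with the secondary endpoints, apart from the AE and SAE safety endpoints. The missing calendar row proves little: viral reactivations (7.2.3) and the steroid discontinuation date (7.1.4) have no row either, yet must be recorded, and the CRFs are not part of the documents.

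Much of this stands. It shows that undercounting is not certain. It does not supply an end date, and it does not override the recording limit that 8.2 applies to events defined in 8.3.

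A reader might infer that both measures are undercounted across the board. The documents do not support that for the stopping rule: counted from first dose, every full course within the permitted spacing is covered. A reader might also infer that early stoppers are mainly patients with complications. Sections 5.2 and 5.5 allow stopping for a related SAE or a change in condition, so a link is possible, but no frequency is given. The rule counts patients, so someone who stops because of a grade 3 infection has already been counted.

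**Conclusion.** The concern holds as an unreconciled conflict between sections that makes undercounting likely but not certain. Its main effect is on the day-100 endpoint, where following 8.2 as written leaves a gap even in patients who complete treatment on the average schedule: about a week or more for day-7 entrants, and at most a few days for day-14 entrants. The gap reaches about two months after a single dose.

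For the stopping rule the exposure is conditional. It needs a last dose before about study day 26, and the loss is at most 26 of 56 days. The fall in stopping probability rests on the assumed share of early stoppers and on evenly spread infections. The one-dose columns are the worst case, and with no early stoppers the stated probabilities are unaffected. The 8-week treatment course makes counting from first dose the more natural reading, but 8.7 does not say so.

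**What to change.** In 8.2, 6.3 and 7.2.2, state that BMT CTN grade 3 infections are collected for every treated patient, whatever the attribution and whether or not AAT was stopped, through the latest of study day 56, HCT day 100 and 30 days after the last dose. Add an infection row to the 6.3 calendar. In 8.7, state which dose the 8 weeks are counted from. If it is not the first dose, extend the collection window to match.

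The cost is a calendar row, a CRF field and a little more data entry. The 6.3 calendar already has assessments at least every other week to HCT day 100, so no visits are added if the 8 weeks run from first dose. This is a cheap improvement.

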### 8.3 Definitions

#### 8.3.1 Adverse Event

An adverse event (AE) is any untoward medical occurrence in a patient receiving study treatment and which does not necessarily have a causal relationship with this treatment. An AE can be any unfavorable and unintended sign (including an abnormal laboratory finding), symptom, or disease temporally associated with the use of an experimental intervention, whether or not related to the intervention.

- Diagnostic and therapeutic non-invasive and invasive (i.e., surgical) procedures will not be reported as adverse events. However, the medical condition for which the procedure was performed must be reported if it meets

the definition of an adverse event unless it is a pre-existing (prior to protocol treatment) condition.

- Event reporting for GVHD treatment protocols can be complicated and confusing for investigators, data managers, and regulatory oversight bodies because patients typically develop numerous complications as part of the typical treatment course not related to study therapy. Furthermore, transplant-related complications often occur both simultaneously and in series, as one complication leads to a series of downstream events. Therefore, a well-conceived event reporting plan separates background transplant and GVHD noise as might be seen with any transplant where GVHD develops from study related events that are relevant to patient safety. On this study, we will not report CTCAE grade 1 and 2 adverse events (which make up the majority of events) unless the investigator determines the event should be reported to protect subject safety.
- It is common for HCT recipients to experience multiple complications as part of the transplant itself that are unrelated to exposure to investigational agents. Symptoms of the original or targeted disease are not to be considered adverse events for this study except that all BMT CTN grade 3 infections will be reported (see Appendix B). Symptoms related to the conditioning regimen or GVHD will not be reported unless the event is serious (see section 8.3.2) and considered by the investigator to be possibly, probably, or definitely related to AAT. Events that are unlikely or unrelated to AAT are not required to be reported. Reporting of such events should include the investigator's assessment as to whether the event should be attributed to any of the HCT procedure itself, GVHD, exposure to immunosuppressive agents other than AAT, and AAT. An event may be attributable to all, some, or one of these categories.
- Abnormal laboratory values or test results constitute adverse events only if they induce clinical signs or symptoms or require therapy and otherwise meet the criteria for a reportable adverse event as defined above. They are to be captured under the signs, symptoms or diagnoses associated with them.

